## 5. INTRODUCTION

Multiple approaches should be sought to mitigate the clinical and public health impact of COVID-19. While several approaches are being investigated with an aim to lower viral load and develop vaccines, an approach to improving respiratory function in COVID-19 patients with respiratory failure is urgently needed. Brexanolone (Zulresso™) is an FDA-approved intravenous (IV) infusion for the treatment of postpartum depression (PPD) in adults. Extensive safety experience in Intensive Care Unit (ICU) was gained during development of a separate indication for super-refractory status epilepticus (SRSE). Based on its unique pharmacology targeting multiple subtypes of GABAA receptors, brexanolone has the potential to attenuate the impact of COVID-19 in ventilated patients through multiple mechanisms of action. Preclinical evidence to date suggests that brexanolone is likely to have the following beneficial effects in the clinic: anti-inflammatory and fluid clearance effects via direct action on GABAA receptors located in human alveolar epithelial cells; anti-inflammatory and antiviral effects via inhibition of toll-like receptors and reduction in proinflammatory cytokines; and direct effects on pulmonary function through direct effects on smooth muscle in the lung, reducing shunting and improving partial pressure of arterial oxygen (PaO2).

Severe forms of infection with SARS-CoV-2 produce significant impairment of respiratory function, including acute lung inflammation and acute respiratory distress syndrome (ARDS) (Wujtewicz 2020). Although epidemiological data are rapidly evolving, preliminary reports show that pulmonary impact severe enough to warrant critical care treatment is occurring in 3 to 6% of infected patients (CDC COVID-19 Response Team 2020; Wujtewicz 2020). Data from United Kingdom and from Seattle both suggest that of patients with COVID-19 in critical care, >75% require mechanical ventilation and up to approximately 50% do not survive (Bhatraju 2020; ICNARC 2020). The respiratory symptoms associated with morbidity are driven by factors including vasoconstriction, pulmonary edema, and inflammation secondary to cytokine activation. In addition to viral-induced respiratory trauma, ventilator support that is provided to address ARDS can also exacerbate lung damage and lead to a negative spiral that further contributes to morbidity and mortality.

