### 12.2.1. Adverse Event Definition

An AE is any untoward medical occurrence in a patient or clinical investigation participant administered a pharmaceutical product and that does not necessarily have a causal relationship with this treatment. An AE can therefore be any unfavorable and unintended sign (including an abnormal laboratory finding), symptom or disease temporally associated with the use of a medicinal (investigational) product whether or not related to the medicinal (investigational) product. In clinical studies, an AE can include an undesirable medical condition occurring at any time, including baseline or washout periods, even if no study treatment has been administered.

A TEAE is defined as an adverse event with onset after the start of IP, or any worsening of a pre-existing medical condition/adverse event with onset after the start of IP and throughout the study. The term IP includes any Sage IP, a comparator, or a placebo administered in a clinical trial.

Laboratory abnormalities and changes from baseline in vital signs, and ECGs are considered AEs if they result in discontinuation or interruption of study treatment, require therapeutic medical intervention, meet protocol specific criteria (if applicable) or if the investigator considers them to be clinically significant. Any abnormalities that meet the criteria for an SAE should be reported in an expedited manner. Laboratory abnormalities and changes from baseline in vital signs and ECGs that are clearly attributable to another AE do not require discrete reporting (eg, electrolyte disturbances in the context of dehydration, chemistry and hematologic disturbances in the context of sepsis).

Participants who discontinue the IP due to an AE, regardless of investigator-determined causality, should be followed until the event is resolved, considered stable, or the investigator determines the event is no longer clinically significant. Any AEs that are unresolved at the participant's last AE assessment in the study are followed up by the investigator for as long as medically indicated, but without further recording in the CRF. The sponsor or its representative retains the right to request additional information for any participant with ongoing AE(s)/SAE(s)/AESIs at the end of the study, if judged necessary.

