## 13.8. Sample Size and Power

The sample size of approximately 100 participants would provide 80% power to detect a treatment difference of 27% in proportions of the primary endpoint of participants being alive and free of respiratory failure at Day 28, assuming the proportion is 50% for the placebo group and 77% for the brexanolone group.

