## 5. STUDY DESIGN

### 5.1. Overall Design

This is a randomized, double-blind, placebo-controlled study designed to evaluate treatment with brexanolone in approximately 100 participants with ARDS due to COVID-19. Participants and their family or caregivers, clinicians, site staff, and sponsor personnel will be masked to treatment allocation.

Participants with ARDS and SARS-CoV-2 infection who give informed consent (or for whom consent is given by a proxy) and who are currently intubated and receiving mechanical ventilation as part of standard of care or who are on an immediate clinical plan to receive such intervention will be eligible for screening. All participants must have mechanical ventilation in place prior to randomization. Eligible participants will be stratified by age (<70 or  $\geq$ 70 years) and randomized 1:1 within each stratum to receive either brexanolone plus standard of care or placebo plus standard of care.

Participants will receive continued standard of care in addition to a continuous intravenous (IV) infusion of investigational product (IP) – brexanolone or placebo for 60 hours. The infusion must be initiated within 6 hours from the time of randomization. The blinded 60-hour infusion will be administered at a dose of 70 mcg/kg/h for 58 hours followed by a 2-hour taper at 35 mcg/kg/h. Transfer out of the ICU is not an indication to discontinue the infusion of investigational product.

Brexanolone may potentiate the sedative effects of co-administered anesthetics. During IP infusion, if sedation levels are deeper than intended, the dose(s) of sedative anesthetics should be titrated to the desired effect rather than adjusting the dose of IP (see Section 7.4 of the study protocol for additional details).

Dose adjustment is permitted in the event that a participant is experiencing unplanned sedation/somnolence when no longer on any sedating agents or if the participant experiences an intolerable adverse event (AE) determined by the investigator to be related to IP. Details regarding dose adjustment criteria and procedures are provided in Section 7.4 of the study protocol.

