## 5.2. Sample Size and Power

The sample size of approximately 100 participants would provide 80% power to detect a treatment difference of 27% in proportion of participants alive and free of respiratory failure at Day 28. The sample size is computed assuming proportion of 50% for the placebo group and 77% for the brexanolone group using Chi-square test with a two-sided Type I error rate (alpha) of 0.05.

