#### 8.4.1. Adverse Events

Adverse events will be coded using Medical Dictionary for Regulatory Activities (MedDRA) Version 23.0 or higher. A treatment-emergent adverse event (TEAE) is defined as an adverse event with onset after the initiation of IP. The analysis of adverse events will be based on the concept of TEAEs.

If the date of an adverse event is incomplete and an unambiguous determination could not be made with respect to its onset time versus the first dose of IP and/or last dose of IP, the adverse event will be assumed to be a TEAE and a treatment period TEAE. For imputation of missing AE dates, please refer to Appendix A.

The incidence of all TEAEs and non-serious TEAE's will be separately summarized by SOC and preferred term PT. In addition, summaries will be provided by maximum severity (mild, moderate, severe, life-threatening, death) and by relationship (related, not related) to IP. Any TEAEs leading to discontinuation of treatment or withdrawal from the study and any treatment-emergent serious adverse events will also be summarized, sorted by descending frequency in SOC and PT.

For maximum severity, participants will be counted only once within each SOC and PT at the maximum severity in the following order: severe > moderate > mild; an AE with missing severity will be omitted from severity presentation. A participant will be counted only once within each SOC and PT at the strongest relationship to IP in the following order: related > not related. The incidences will be presented by descending frequency of SOC in the brexanolone group and then, within a SOC, by descending frequency of PT based on the participant count, and in alphabetical order of PT if the incidence within a PT is a tie.

The following table documents events considered to be AESI in this study, and the MedDRA preferred terms and lower-level terms (i.e., LLTs) in the right-hand column will be used to screen adverse events for possible AESI status. Where LLTs are specified, they take precedence in the determination of AESI's; when LLTs are left unspecified, it is understood that MedDRA preferred terms will take precedence:

AESI Term	MedDRA Preferred Term(s)
Loss of Consciousness	
 
1. Loss of consciousness
 
2. Altered state of consciousness
 
3. Syncope
 

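### Crude end-of-study percentages for non-fatal adverse events can be distorted when mortality differs by arm, and no readable table shows follow-up time or a fixed early window

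*SAP*

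**What the plan says.** - **Measure.** SAP 8.1 summarizes the presence of an adverse event by counts and percentages. SAP 8.4.1 states: "The incidence of all TEAEs and non-serious TEAE's will be separately summarized by SOC and preferred term PT". Its severity and relationship summaries count a participant once per SOC and PT. Special-interest events (AESIs) follow the same layout. SAP Table 3 marks adverse events under incidence only.
- **Window.** Protocol 12.2.1 takes in events "with onset after the start of IP and throughout the study". SAP 8.2.1 places the last visit at Day 28±3. The infusion lasts 60 hours.
- **Mortality.** Protocol Section 5 says of COVID-19 patients in critical care that "up to approximately 50% do not survive". SAP 8.3.3 reports the Day 28 proportion of deaths by arm. SAP 6.1.4 drops the Kaplan-Meier analysis.
- **Follow-up time.** SAP 8.2.7 summarizes infusion duration, not adverse-event follow-up. SAP 8.4.1 mentions a treatment-period TEAE in its rule for incomplete dates, but no readable table uses it.
- **Role.** Incidence of treatment-emergent events is a secondary endpoint (Protocol 6.2.2) and serves the safety objective (Protocol 6.1.2).

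**The concern.** A participant who dies on Day 6 can show an event for 6 days; a survivor can do so for about 28. Both add one to the denominator. If one arm survives longer, its participants have more days in which a non-fatal event can be seen, and its crude percentage can rise without any higher event rate.

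This matters most where deaths do not enter the count. The non-serious table contains none. Delirium and reintubation are AESIs, and Protocol 7.4.2 names an increased risk of either as a reason to stop enrollment. A participant must also live long enough to be extubated before reintubation is possible. From the planned tables a reader cannot separate a difference in event rate from a difference in follow-up.

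**Working it through.** **1. The plan's own figure.** Inputs: 1:1 allocation, "assuming proportion of 50% for the placebo group and 77% for the brexanolone group", and "using Chi-square test with a two-sided Type I error rate (alpha) of 0.05" (SAP 5.2). Pooled p = 0.635.

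n per arm = [1.96·√(2·0.635·0.365) + 0.842·√(0.5·0.5 + 0.77·0.23)]² / 0.27² = 48.7, so 49 per arm, 98 in total. Power at 50 per arm is 81%. The stated 80% with about 100 participants reproduces. These rates are for the composite of alive and free of respiratory failure. The documents give no mortality assumption by arm.

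**2. Non-fatal events under equal hazards.** Let I be the 28-day event risk absent death (the same in both arms, so no true excess) and m the 28-day mortality. With constant hazards a = −ln(1−I)/28 and d = −ln(1−m)/28:

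crude incidence = a/(a+d) × [1 − (1−I)(1−m)]

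Example with I = 30%, so a = 0.01274 per day:
- m = 50%: d = 0.02476; 0.340 × 0.650 = 22.1%.
- m = 23%: d = 0.00933; 0.577 × 0.461 = 26.6%.

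Brexanolone minus placebo, in points (I and the mortality figures are assumptions):

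| Mortality, placebo vs brexanolone | I=10% | I=30% | I=50% | I=80% |
|---|---|---|---|---|
| 50% vs 40% | +0.6 | +1.8 | +2.8 | +3.9 |
| 50% vs 23% | +1.6 | +4.5 | +7.2 | +9.9 |
| 50% vs 60% | −0.7 | −1.9 | −3.0 | −4.3 |

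Mean time alive, m/d, is 20.2 vs 24.6 days at 50% vs 23%. Front-loaded deaths (daily weights proportional to exp(−day/8) or exp(−day/14)) give a similar size: a 40% event appears in 26-28% vs 34-35%.

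**3. Early events.** If the event risk lies in the first 3 days only, the 50% vs 23% differences are +0.2, +0.6 and +1.0 points at I = 10%, 30% and 50%. Mean time alive in that window, [1 − exp(−3d)]/d, is 2.89 vs 2.96 days.

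**4. Higher event hazard in those who die.** Let deaths be uniform over Days 3 to 28, and let participants who die have k times the survivors' hazard. Incidence = (1−m)·I + m × mean of [1 − exp(−k·a·t)]. At 50% vs 23%, for I = 10%, 30% and 50%:
- k = 1: +1.2, +3.4, +5.2 points
- k = 2: −0.2, −0.4, −0.2 points
- k = 3: −1.6, −3.4, −3.7 points

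**5. Tables that count deaths.** If every death enters as a fatal event, any-event incidence is 1 − (1−I)(1−m). At I = 30% it is 65.0% placebo vs 46.1% brexanolone for 50% vs 23% mortality, and 65.0% vs 72.0% for 50% vs 60%. The direction is the opposite of step 2.

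**6. What a whole-study rate would do.** Under constant equal hazards, first events per participant-day give a ratio of 1.00. With equal risk confined to the first 3 days, 50% vs 23% mortality and the front-loaded deaths of step 2, the same rate gives 0.79 to 0.83, because survivors add event-free late days. A true early excess of 36% vs 30% (ratio 1.20) shrinks to 1.03-1.07.

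**7. Noise.** At 50 per arm the standard error of a difference is √(0.22·0.78/50 + 0.26·0.74/50) = 8.5 points, and 9.8 points for 37% vs 45%.

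**The case against.** A reader might infer that a life-saving drug will show more adverse events and a lethal one fewer. The documents do not support that as a general statement. An event that results in death is an SAE (Protocol 12.2.2), fatal events on the common-ICU list are still reported as SAEs (Protocol 12.2.6), and the SAP severity summary has a death category. In the all-event and serious-event tables the direction therefore reverses (step 5).

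A reader might also take 50% vs 77% as mortality of 50% vs 23%. That requires no survivor in either arm to be on respiratory support at Day 28. It is a corner case, not a planning assumption.

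Further objections stand in part:
- A constant hazard to Day 28, equal in those who die and those who survive, is doubtful after a 60-hour infusion in intensive care. After discharge only limited assessments are made by phone (Protocol 7.1). About twice the hazard in those who die cancels the effect.
- No hypothesis test on adverse events is specified, mortality is shown by arm, and adverse events of participants who died are listed separately. A lethal effect is not hidden.
- The distortion is at most about one standard error at 50 per arm, and recruitment stopped early (SAP 6.1), so estimates will be noisier still.
- A single whole-study person-time rate could mask an early, infusion-related signal (step 6).

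These points limit the size and rule out a simple rate as the remedy. They do not supply the missing follow-up time or early-window table.

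**Conclusion.** The concern holds for non-fatal events and is conditional. When mortality differs by arm, crude end-of-study percentages in the non-serious and AESI tables can be distorted, and nothing in the readable text lets a reader see this. The size is about 1 to 4 points at 50% vs 40% mortality and up to about 10 points at 50% vs 23%, for 28-day event risks of 10% to 80%. These figures assume constant hazards, equal event hazards in those who die and those who survive, and no other dropout. None of these assumptions, nor the mortality figures by arm, is stated in the plan. For events in the first days the distortion is about 1 point or less. Its sign is uncertain if those who die have more events beforehand. Redacted SAP text could contain more. This is a gap in descriptive safety reporting; it does not invalidate the safety analysis.

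**What to change.** In SAP 8.4.1:

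1. Keep the crude tables.
2. Add a table of TEAEs and AESIs with onset in a fixed early window, for example Hour 0-72. This matches the hourly visit windows in SAP Table 2 and gives the treatment-period TEAE a definition and a use. Follow-up is nearly equal there.
3. For the overall non-serious, non-fatal SAE and AESI rows, add by arm the participant-days at risk and first events per 100 participant-days. Time at risk runs from IP start to first event of that type, death, study exit or Day 28. Split it into the early window and the remainder to Day 28. Show fatal events separately.
4. State that these are descriptive supplements, and that a whole-study rate must not be used to discount an early excess.

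Cost: SAP wording and a few extra columns. Event onset and death dates and times are already collected (Protocol 12.2.5 and 11.1.7). The rates still assume a roughly constant hazard within each period.

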## 7.4. Dose Adjustment Criteria

Because brexanolone is a GABAA receptor positive allosteric modulator, it is possible that the sedating properties of co-administered anesthetics may be potentiated in the presence of brexanolone. Thus, during brexanolone infusion, lower doses of co-administered sedative agents may achieve the same anesthetic effects. During IP infusion, if sedation levels are deeper than intended, the dose(s) of sedative anesthetics should be titrated to the desired effect rather than adjusting the dose of IP.

After the anesthetic agents are stopped, patients will remain sedated for varying amounts of time as the anesthetic agents wash out of lipid tissues. Additionally, in patients who are candidates for extubation, it is common to continue mild sedation using drugs that do not affect respiratory drive (eg, dexmedetomidine) after discontinuing the anesthetic agent(s), in order to facilitate a spontaneous breathing trial.

In the scenario that a participant is experiencing unplanned sedation/somnolence when no longer on any sedating agents, but still receiving blinded IP, the IP infusion may be stopped or the dose may be reduced to 35 mcg/kg/h until the symptoms resolve.

The IP infusion may also be stopped or the dose may be reduced to 35 mcg/kg/h if the participant experiences an intolerable AE determined by the investigator to be related to IP.

If the infusion is stopped and symptoms resolve, the IP infusion may be resumed at the same or lower dose as clinically appropriate. Each time the decision is made to stop the IP infusion or reduce the dose for AEs, the Richmond Agitation Sedation Scale (RASS) will be administered, and if RASS ≥ -3, the Confusion Assessment Method for the intensive care unit (CAM-ICU) will be administered as well (see Section 12.1.7).

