**12.2.5. Recording Adverse Events**

Adverse events spontaneously reported by the participant and/or in response to an open question from the study personnel or observed will be recorded during the study at the investigational site. The AE term should be reported in standard medical terminology when possible. For each AE, the investigator will evaluate and report the onset and resolution (date and time), intensity, causality, seriousness criterion(ia), action taken, and outcome (if applicable), and whether the AE resulted in IP dose reduction, discontinuation of the IP or withdrawal from the study.

Intensity will be assessed according to the guidelines for the National Cancer Institute Common Terminology Criteria for Adverse Events (CTCAE) Version 5.0. The CTCAE provides a grading (severity) scale for AEs, with unique clinical descriptions of severity based on the general guidance listed below:

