#### 13.6.1. Adverse Events

AEs will be coded using Medical Dictionary for Regulatory Activities (MedDRA) Version 23.0 or higher. A treatment-emergent adverse event (TEAE) is defined as an AE with onset after the start of IP. The analysis of AEs will be based on the concept of TEAEs. The incidence of TEAEs will be summarized by System Organ Class and preferred term. In addition, summaries will be provided for TEAEs Grade 3 and above per CTCAE guidelines and by causality (related, not related) to IP.

Any TEAEs leading to IP discontinuation, dose reduction, or study withdrawal and any treatment-emergent SAEs and AESIs will be summarized.

All AEs, SAEs, and AESIs (including those with onset or worsening before the start of IP) through the end of the study will be listed.

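### SAP 8.4.1 plans no by-arm summary of TEAEs that led to an IP dose reduction, which Protocol 13.6.1 requires, or to a temporary interruption, which neither document plans

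*SAP*

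**What the plan says.** - **Permitted responses.** Protocol 7.4 names two triggers for changing the infusion: unplanned sedation or somnolence in a participant off all sedating agents, and an intolerable AE that the investigator relates to IP. In either case the infusion may be stopped or its rate lowered. A stop need not be final: "If the infusion is stopped and symptoms resolve, the IP infusion may be resumed at the same or lower dose as clinically appropriate".
- **Interruption as a separate idea.** Protocol 12.2.1 counts laboratory, vital-sign and ECG abnormalities as AEs "if they result in discontinuation or interruption of study treatment", among other conditions.
- **What is recorded.** Protocol 12.2.5 collects a general action-taken item for each AE, and also "whether the AE resulted in IP dose reduction, discontinuation of the IP or withdrawal from the study". Interruption is not named, and the response options of the action-taken item are not given.
- **Protocol summaries.** Protocol 13.6.1 commits to summarizing "Any TEAEs leading to IP discontinuation, dose reduction, or study withdrawal", along with treatment-emergent SAEs and AESIs.
- **SAP summaries.** SAP 8.4.1 has a shorter list: "Any TEAEs leading to discontinuation of treatment or withdrawal from the study and any treatment-emergent serious adverse events will also be summarized". Dose reduction is not in it.
- **Declared changes.** The visible entries of SAP 6.1 cover the per-protocol population, concomitant medications, efficacy analyses, tipping-point analyses and the interim analysis. None mentions TEAEs leading to dose reduction. Some entries are redacted.
- **Exposure.** SAP 8.2.7 computes exposure duration as infusion end minus start and says that interrupted time is not excluded. SAP 8.2.8 defines adherence as actual over planned total dose.

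**The concern.** Safety is the trial's secondary objective, and TEAE incidence is a secondary endpoint in the protocol. The protocol expects possible potentiation of sedation and makes unplanned sedation or somnolence an AESI. A reader of the safety results will ask how often an AE led the site to change the infusion, and whether that differed by arm. There are three possible changes: permanent stop, reduction, and stop with resumption. The SAP plans a table only for discontinuation, the term that naturally describes the first. One of the other two was promised in the protocol, and the other was never planned. The final tables could therefore describe tolerability of the infusion without a count for two of the responses that Protocol 7.4 allows.

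**Working it through.** The plan states no figure on this point, so there is none to reproduce. The check has three steps.

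**Step 1. Follow each permitted response through both lists.**

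| Response to the AE (Protocol 7.4) | Protocol 13.6.1 | SAP 8.4.1 |
|---|---|---|
| Stopped and not resumed | IP discontinuation | Discontinuation of treatment |
| Rate reduced, infusion continues | Dose reduction | None |
| Stopped, resumed at a lower dose | Fits dose reduction | None |
| Stopped, resumed at the same dose | None | None |

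Restoring the protocol's list would fill the second and third rows but not the fourth. One uncertainty applies to the last two rows: SAP 8.4.1 does not say that discontinuation means permanent, so a temporary stop could be coded there. That would mix two different outcomes in one table.

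**Step 2. Ask whether exposure or adherence can stand in.**

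Inputs: 70 mcg/kg/h for 58 hours, then 35 mcg/kg/h for 2 hours (Protocol 10.5).

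Planned total dose = 70 × 58 + 35 × 2 = 4060 + 70 = 4130 mcg/kg.

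For a pause of h hours during the 70 mcg/kg/h phase that is not made up, adherence = (4130 − 70h) / 4130. The pause lengths below are assumptions.

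| Pause | Adherence if not made up | Exposure duration |
|---|---|---|
| 1 h | 98.3% | 60 h |
| 2 h | 96.6% | 60 h |
| 6 h | 89.8% | 60 h |
| 12 h | 79.7% | 60 h |

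Three different histories give the same adherence as the 6-hour pause:
- a 6-hour pause loses 70 × 6 = 420 mcg/kg, so (4130 − 420) / 4130 = 89.8%;
- 12 hours at 35 instead of 70 mcg/kg/h loses 35 × 12 = 420 mcg/kg, so 89.8%;
- a permanent stop at hour 53 delivers 70 × 53 = 3710 mcg/kg, so 3710 / 4130 = 89.8%.

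If the 6-hour pause is made up, adherence is 100% and duration is 66 hours. Adherence can hint at lost dose. It cannot say whether the cause was a pause, a reduction or an early stop, and it does not link the loss to an AE. Exposure duration leaves the pause in. Total exposure is set to zero for placebo participants who received no brexanolone (SAP 8.2.7), so it cannot compare the arms.

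**Step 3. Ask whether another safety output gives the count.**

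The all-TEAE, severity, relationship and AESI tables count the event but not what was done with the infusion. RASS is administered at each decision to stop or reduce, but unscheduled values go to listings (SAP 8.4.6). CAM-ICU is only listed (SAP 8.4.7). No visible output gives a by-arm count of AE-driven reductions or interruptions.

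**The case against.** The strongest reply is that the AEs themselves are reported. SAP 8.4 summarizes safety by treatment group. An event that prompts a pause enters the all-TEAE table, the maximum-severity table and the relationship table. Sedation and somnolence terms also enter the AESI table, and an intolerable AE must be judged related before Protocol 7.4 applies, so it falls in the related category. All AEs are listed. This stands. A reader might infer that these events are hidden by arm, or that the active arm will look better tolerated than it is. The documents support neither inference: the events are counted, and nothing shows that brexanolone would have more pauses than placebo.

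A second reply is that the situation is narrow. Protocol 7.4 directs the site to titrate the sedatives first, and stopping or reducing IP for sedation applies only once the participant is off them. This also stands. The documents give no frequency, so stop-and-resume cannot be called a main tolerability response.

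A third reply is that the study was ended early and SAP 6.1 simplified some analyses on purpose. That is a fair reason to keep displays few. It explains less well why discontinuation keeps its table while dose reduction, promised in the protocol, drops out with no visible note.

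Finally, the list of displays in SAP Appendix B is not shown, parts of SAP 6.1 are redacted, and the wording of the treatment-completion question on the CRF is not given. Absence from the visible text does not prove that no such table exists, and how a paused participant would be classed cannot be settled from the documents.

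**Conclusion.** The point holds as a limited reporting gap in the visible text, in two parts. First, SAP 8.4.1 drops the summary of TEAEs leading to dose reduction that Protocol 13.6.1 requires, with no visible declaration. Second, neither document plans a summary of TEAEs leading to interruption, although Protocol 7.4 allows stop-and-resume and Protocol 12.2.1 names interruption beside discontinuation. The loss is the by-arm count by action taken, not the events.

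The size cannot be estimated. Purely as an illustration, if 10% on brexanolone and 2% on placebo had an AE-driven pause that was resumed at the same dose, 50 per arm would give 5 against 1 participants (0.10 × 50 and 0.02 × 50). These participants would appear in the TEAE tables but in no action table, provided a temporary stop is not coded as discontinuation. Both rates are assumptions, and the real difference could be zero or run the other way. This is a minor improvement to the safety reporting and does not touch the efficacy analysis.

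**What to change.** In SAP 8.4.1, by actual treatment received in the Safety Set:

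- restore the summary of TEAEs leading to IP dose reduction, or declare and justify its removal in SAP 6.1;
- add a summary of TEAEs leading to temporary IP interruption, taken from the action-taken item of Protocol 12.2.5 and supported by recorded administration times (Protocol 9.4) where available;
- state, for reporting purposes, that discontinuation means the infusion was not resumed;
- show participants with an AE-driven interruption, reduction or discontinuation separately and combined.

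The cost is one or two more tables. Before they are specified, the action-taken response options must be confirmed to distinguish interruption from discontinuation. If they do not, interruptions would have to be derived from infusion stop and restart times. Protocol 9.4 places administration times in the source documents, and no visible text confirms that stop and restart times are in the analysis database. The change affects reporting only and alters nothing in patient care.

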**Table 2: Common Terminology Criteria for Adverse Events**

Grade	Criteria
1	Mild; asymptomatic or mild symptoms; clinical or diagnostic observations only; intervention not indicated
2	Moderate; minimal, local, or noninvasive intervention such as packing or cautery indicated, limiting age-appropriate instrumental activities of daily living (ADL)
3	Severe; or medically significant but not immediately life-threatening; hospitalization or prolongation of hospitalization indicated; disabling; limiting self-care ADL

Grade	Criteria
4	Life-threatening consequences; urgent indications indicated
5	Death related to adverse event

It is important to distinguish between seriousness and severity. Severity is a measure of intensity whereas seriousness is defined by the criteria under Section 12.2.2. An AE of severe intensity may not necessarily be considered serious.

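### The SAP's maximum-severity rule does not rank life-threatening or fatal events, and two adverse-event summaries required by the protocol are missing from SAP 8.4.1 without a declared change

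*SAP*

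**What the plan says.** SAP 8.4.1 sets out the severity display: "summaries will be provided by maximum severity (mild, moderate, severe, life-threatening, death) and by relationship (related, not related) to IP". The next paragraph but one gives the counting rule. Within each system organ class (SOC) and preferred term (PT), a participant is counted once, "at the maximum severity in the following order: severe > moderate > mild".

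The protocol grades events on a five-level scale. Section 12.2.5 states: "Intensity will be assessed according to the guidelines for the National Cancer Institute Common Terminology Criteria for Adverse Events (CTCAE) Version 5.0". Its Table 2 puts life-threatening consequences at Grade 4 and defines Grade 5 as "Death related to adverse event".

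Protocol 13.6.1 asks for two summaries that matter here. On severity, "summaries will be provided for TEAEs Grade 3 and above per CTCAE guidelines". On actions taken, it lists "Any TEAEs leading to IP discontinuation, dose reduction, or study withdrawal" for summary. The matching SAP 8.4.1 sentence covers "Any TEAEs leading to discontinuation of treatment or withdrawal from the study". Dose reduction is not in it, and readable SAP 8.4.1 names no Grade 3-and-above summary.

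SAP 6.1 is where changes from the protocol are recorded. Its overview gives three analyses as dropped because of early termination: Kaplan-Meier, tipping-point and interim. None of its readable subsections mentions an adverse-event table.

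**The concern.** A maximum-severity table needs a complete ranking. Without one, the programmer has to guess how to place a participant with events of different grades in the same SOC or PT, and the written rule says nothing about the two grades that matter most. Taken literally, it can show a participant below their worst event.

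The two missing summaries add to this. The maximum-severity table is the only severity display left in readable SAP 8.4.1. For actions taken, Protocol 7.4 names dose reduction as one of two responses to unplanned sedation or to an intolerable related event, and Protocol 12.2.5 has it recorded for each event. Yet no by-arm summary described in the readable SAP links events to dose reductions. Safety is the trial's secondary objective, and unplanned sedation is an event of special interest.

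**Working it through.** The plan states no figure on this point, so there is none to reproduce. No sample-size or power value enters the check.

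**Step 1. Protocol 13.6.1 against SAP 8.4.1 (readable text)**

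| Item | Protocol | SAP 8.4.1 |
|---|---|---|
| Severity scale | Grades 1 to 5 (12.2.5, Table 2) | Five categories in the table, three in the ranking |
| Grade 3 and above | Required | Not named |
| Leading to discontinuation | Required | Kept |
| Leading to study withdrawal | Required | Kept |
| Leading to dose reduction | Required | Not named |
| Serious events, events of special interest | Required | Kept |

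**Step 2. What the three-level ranking leaves open**

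Within one SOC or PT, a participant with at least one graded event has some non-empty set of the five grades.

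- All possible sets: 2^5 − 1 = 31.
- Sets with more than one grade, which need a ranking: 31 − 5 = 26.
- Of those 26, sets using only Grades 1 to 3, which the rule resolves: 3 pairs + 1 triple = 4.
- Sets left unresolved: 26 − 4 = 22.

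**Step 3. What a literal program would do**

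Suppose the maximum is taken only over the three ranked levels.

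- Sets shown below the worst grade contain at least one of Grades 4 and 5 and at least one of Grades 1 to 3: (2^2 − 1) × (2^3 − 1) = 3 × 7 = 21.
- Sets whose worst event is Grade 3 or higher: 31 − (2^2 − 1) = 28.
- Of those 28, sets that would be shown below Grade 3 contain Grade 1 or 2, contain Grade 4 or 5, and do not contain Grade 3: 3 × 3 = 9. Grade 1 with Grade 4 is an example.

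**Step 4. With the five-level ranking**

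All 31 sets get one category, and none is shown below its worst grade. Within a single SOC or PT, the Grade 3-and-above count equals severe + life-threatening + death, for 28 of 28 sets. This does not give the number of participants with any such event. The rule counts once per SOC and PT, so adding across SOCs can count one participant several times.

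**Step 5. Can dose reductions be recovered elsewhere?**

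Not from the summaries described in the readable SAP. Exposure duration (8.2.7) runs from start to end of infusion and does not subtract interruptions. Adherence (8.2.8) is actual over planned total dose, so it mixes reductions with early stops and links neither to an event.

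**The case against.** The strongest case on the other side is that this is an incomplete sentence in a section whose intent is clear. Life-threatening and death are named categories of the table, and a death row that excluded participants who also had a severe event would make little sense. Most programmers would extend the order correctly. That stands, and it means that the defect is an ambiguity with a risk of under-grading.

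A reader might infer that the worst events will be misreported. The documents do not support that. SAP 8.4.1 keeps a summary of treatment-emergent serious events, lists all adverse events, and provides a separate listing for participants who died. SAP 8.3.3 compares all-cause mortality by arm.

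A reader might also want a number of participants affected. None can be given: the documents contain no adverse-event rates, do not say how often a fatal event shares an SOC with a milder one, and give no final sample size after early termination.

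Three more points go to the other side:

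- Two of the three action summaries, discontinuation and withdrawal, are kept. Only dose reduction is missing. Dose interruption is not in the protocol's list, so its absence is no departure from the protocol.
- Events with missing severity are left out of the severity display only. They stay in the all-TEAE table, and how to show them is a matter of convention.
- Once the ranking is complete, Grade 3-and-above counts within each SOC or PT follow by addition. What stays lost is the participant-level total.

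The omissions themselves can be confirmed only for readable text. The content of SAP Appendix B (list of displays) is not shown and parts of SAP 6.1 are redacted, so a display or a declared change could sit there.

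**Conclusion.** The point holds in a limited form. The ranking in SAP 8.4.1 does not fit the five-category table that it is meant to fill. It leaves 22 of 26 multi-grade patterns unresolved and, on a literal reading, under-grades 21. How often those patterns would occur is unknown. Two summaries required by Protocol 13.6.1 are absent from readable SAP 8.4.1, and the readable part of SAP 6.1 declares neither change.

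The consequence is confined to the maximum-severity table and to events managed by dose reduction. The reporting of deaths and serious events does not depend on this rule. The conclusion assumes that nothing in Appendix B or in the redacted parts of SAP 6.1 supplies the missing displays or declares their removal. The contradiction in the ranking is visible within SAP 8.4.1 itself and does not rest on that assumption.

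**What to change.** In SAP 8.4.1, replace the ranking with: death > life-threatening > severe > moderate > mild.

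Restore the by-arm summary of TEAEs leading to dose reduction. Restore the Grade 3-and-above summary, at least as one row per arm for participants with any TEAE of Grade 3 or higher. If the sponsor prefers to drop either, record and justify that in SAP 6.1, as was done for the other dropped analyses.

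The cost is one corrected line and two short tables. Protocol 12.2.5 already requires both intensity and dose reduction to be recorded for each event, so no new data are needed. SAP Section 2 has the plan finalized before database lock. A change made after lock would have to be documented in the clinical study report.
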